interest are controlled within session, upcoming blocks are not known to experimenter or participant, behavioral metrics are different patterns of decision-making within the same epoch of the task, all task sessions are meaningful to the outcomes of the study, and experimenter-participant interactions are kept to a minimum within the task.

Randomization

We will use computer code to randomize and counterbalance the sequence of blocks within each session. Each session includes six blocks of 30 trials each. Every trial within a block will be either delta-beta stimulation, theta-gamma stimulation, or arrhythmic patterned stimulation. The order of blocks will be randomized for each participant. We will enforce that the first three blocks and last three blocks include each stimulation condition and participants will not receive the same form of stimulation two blocks in a row. This randomization scheme ensures that each type of stimulation is delivered at various temporal phases across the overall session. Within each session, the incentive that is offered for each trial will be randomized and counterbalanced such that an equal number of low (\$2.50, \$3.00, \$3.50, \$4.00) and high (\$4.50, \$5.00, \$5.50, \$6.00) value incentives are offered. Finally, the sequence of receiving stimulation to dlPFC and mPFC over the 3rd and 4th session will be randomized and counterbalanced across participants. In addition, both of the stimulation sessions include conditions of active interest to the investigators and so there will be no systematic bias to devalue one of the sessions. These methods for randomization and counterbalancing will reduce the chances that some unforeseen pattern of TMS or task parameters will systematically bias behavior. Thus, the experimental design has been selected to rigorously support scientific integrity.

Preregistration

The hypotheses of this study that are explicitly described in this protocol will be pre-registered on ClinicalTrials.gov. This ensures that the write-up of all manuscripts that result from this project will be clear to define what was a hypothesized outcome and what findings are unexpected. Furthermore, this process prevents any exploratory findings to be framed as hypothesized findings. By clearly defining these planned analyses, bias is minimized in the analysis of these data.

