9.2 SAMPLE SIZE DETERMINATION

The sample size is 24 participants in the final dataset to be used in analysis. However, to ensure that 24 participants complete the experiment, we conservatively estimate to enroll 50 participants as a ceiling for the sake of IRB approval. The motivation for the sample size of 24 participants in the analysis is explained below. The sample size is determined based on previous experiments from our group: the effect size of previous findings and the reliability of our estimates. Our estimators are precise due to sufficient number of trials per condition with each participant and that the tasks are titrated to the individual.

Primary outcome: Rhythmic TMS to lateral frontal cortex at delta-beta frequency will increase goal-directed behavior relative to arrhythmic TMS.

Previous Data: The planning and refinement of the proposed study was informed by our previous experiments that serve as preliminary data for the proposal. In our previous experiment, we delivered rhythmic TMS to lateral frontal cortex to increase performance in a cognitive control task (Riddle et al. 2020b). In our previous study, there was a significant interaction between TMS site and TMS frequency in a two-way repeated-measures ANOVA such that the improvement in performance in the cognitive control task was site and frequency-specific. The effect size from the partial-eta square was 0.23, and the effect from a dependent t-test was 0.532, with 20 participants. The experimental design of this previous study is similar to the current study in that there are two sites for stimulation (lateral frontal and medial frontal) with two different stimulation frequencies (delta-beta and theta-gamma). Both studies used an arrhythmic condition to control for non-specific effects of TMS.

Sample Size Determination and Power Calculation: Based on this previous effect size, we estimated that our participant count at 24 participants is powered at >95%.

[figure not shown]

Figure 3. Power calculation for the interaction effect in two-way repeated-measures ANOVA modeled as within factors interaction in a two-way ANOVA with partial-eta square of 0.23, and a correlation between variables of 0.77 based on Riddle, Scimeca et al. 2021. Power calculation run using the G*Power software. Proposed number of participants is 24 and is depicted in red.

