9.4 STATISTICAL ANALYSES

9.4.1 GENERAL APPROACH

All testing described below assumes a significance threshold of $p = 0.05$. Analyses will be deemed to be statistically significant if the p -value is less than this threshold. An analysis that does not exceed this threshold will be considered inconclusive. Continuous data will be described using means, standard deviations, and confidence intervals, while categorical data will be described using counts/percentages.

There may be additional covariates included in the analysis. Data will be assessed for normality and, if deemed necessary, corrective procedures will be applied (e.g., log normalization). Based on our previous dataset, we expect that the variables used here will be approximately Gaussian. However, if the distribution of a variable displays a skewed tail and a test for normality fails, then it is justified to use a corrective procedure. This correction will be applied upon consideration of the variables themselves, and not based on the result of the intended analysis.

Data will be collected until 24 participants complete the study and all data is usable. Given that recruitment will be feasible in a convenience sample, we expect to have complete data and all analyses will include the full participant pool. However, if there are technical errors that are not caught in time, then the affected analyses may have less participants. In this scenario, the data for a participant is then completely removed from the analysis.

The effects of stimulation are expected to be transitory, lasting for only a second or two after stimulation. For this reason, stimulation is delivered “online” immediately preceding the time at which the cognitive processes of interest are engaged. During each session, we include a control condition (arrhythmic TMS) that will be subtracted from the conditions of interest (delta-beta TMS and theta-gamma TMS). Therefore, we control for any effects of sequence or time within each session by subtracting each metric of interest from the condition-matched arrhythmic TMS metric. Furthermore, any learning effects from performing the reward-based decision-making task should be stabilized by the 3rd session. These methods are typical

in cognitive neuroscience paradigms. For the reasons listed above, it is unlikely that there will be any effect of sequence or carryover effects between sessions.

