9.4.2 ANALYSIS OF THE PRIMARY OUTCOME (BEHAVIOR)

Goal-directed behavior will be calculated as the average decision to perform the HARD task. The average of the two blocks for each stimulation conditions will be calculated (three stimulation types by two stimulation sites). A two-way repeated-measures analysis of variance (ANOVA) will be performed using within-participant factor of stimulation type (delta-beta TMS versus theta-gamma TMS; each subtracted by session-matched arrhythmic TMS) and within-participant factor stimulation site (dIPFC TMS versus mPFC TMS). We control for the effect of time with a subtraction of delta-beta TMS versus arrhythmic TMS and theta-gamma TMS versus arrhythmic TMS. In other words, four values are submitted to the ANOVA for each participant.

1. Delta-beta TMS to dIPFC minus arrhythmic TMS to dIPFC
2. Theta-gamma TMS to dIPFC minus arrhythmic TMS to dIPFC
3. Delta-beta TMS to mPFC minus arrhythmic TMS to mPFC
4. Theta-gamma TMS to mPFC minus arrhythmic TMS to mPFC

Thus, only differences from our active control, arrhythmic TMS, are considered meaningfully worth interpretation. We hypothesize to find an interaction between stimulation site and stimulation type in the ANOVA. Post-hoc differences will be investigated using Tukey's method to address multiple comparisons. We hypothesize that the predicted interaction will be driven by an increase in goal-directed behavior for delta-beta TMS to dIPFC. Sensitivity analyses will be conducted to evaluate the specificity of these effects: a similar analysis with reward-evaluation as the dependent variable and we do not expect that delta-beta TMS will have any effect on reward-evaluation.

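### The primary and secondary ANOVAs leave out the randomised site order, so a change in the pattern difference between sessions 3 and 4 would enter the error term, and subtracting arrhythmic TMS does not prevent it

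*Combined protocol and SAP*

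**What the plan says.** Section 6.3 states that the order of dlPFC and mPFC stimulation "over the 3rd and 4th session will be randomized and counterbalanced across participants". Each participant's order is therefore known. Within a session there are six blocks, each half contains all three patterns, and "participants will not receive the same form of stimulation two blocks in a row".

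The primary analysis (9.4.2) is a two-way repeated-measures ANOVA of stimulation type by site. Each condition is averaged over its two blocks and the same-session arrhythmic value is subtracted: "In other words, four values are submitted to the ANOVA for each participant". Section 9.4.3 repeats this for coupling. Neither section has a term for site order, session, or the pattern of the preceding block.

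Section 9.4.1 gives reasons: effects should fade within a second or two, the arrhythmic subtraction is said to control sequence and time, and learning should have settled by session 3. It concludes that "it is unlikely that there will be any effect of sequence or carryover effects between sessions". It also allows extra covariates but names none. Section 9.4.5 compares side-effect severity between the dlPFC and mPFC sessions, again without order.

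**The concern.** Within one person, site and session are the same split: whoever has dlPFC in session 3 has mPFC in session 4. Only the randomised order separates the two across people, and the model does not use it. Anything that makes the pattern difference itself depend on the session therefore goes into the residual and, if completers are unevenly split between orders, partly into the estimate. The safeguard the plan names, subtraction of arrhythmic TMS, does not act on the interaction that carries the hypothesis. At stake is the power of the primary and secondary contrasts and, with uneven orders, their bias. The side-effect comparison is more exposed, because it has no within-session control at all.

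**Working it through.** **Inputs.** From 9.2: "The sample size is 24 participants in the final dataset to be used in analysis"; "The effect size from the partial-eta square was 0.23, and the effect from a dependent t-test was 0.532, with 20 participants"; and "a correlation between variables of 0.77". From 9.4.1: alpha 0.05, taken as two-sided. The session shift (delta) and the carry-over fraction (L) are not in the documents; the values below are assumptions.

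**The plan's power figure.** f² = 0.23/0.77 = 0.299. With noncentrality N·m·f²/(1−ρ) = 24 × 2 × 0.299/0.23 = 62.3, power exceeds 99.9%, so the stated figure of over 95% is reproduced. The interaction is, however, a single contrast per person, and its power depends on dz. Partial eta-squared 0.23 with n = 20 gives dz = √(0.299 × 19/20) = 0.533, the same effect as the quoted 0.532. At dz 0.532 and n = 24, power is 70.4% on 23 df. That gap is a separate matter; 70.4% is the reference here.

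**What cancels.** Write DB, TG and A for the three patterns. At each site, (DB − A) − (TG − A) = DB − TG. The interaction is (DB − TG at dlPFC) − (DB − TG at mPFC). A is absent. An amount added to every pattern in a session also drops out: simulated additive session effects of 1 and 5 contrast SDs left the contrast SD at 1.00 and power at about 71%.

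**What does not cancel.** Suppose DB − TG is larger by delta in session 3 than in session 4. The contrast becomes effect + delta for dlPFC-first and effect − delta for mPFC-first. In contrast-SD units at 12:12, the expected residual variance is 1 + delta² × 24/23, while the true standard error of the mean stays at 1/√24 = 0.204. Simulating the planned test:

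| delta (assumed) | SD multiplier | power, no order term | size, no order term | power, order term (22 df) |
|---|---|---|---|---|
| 0 | 1.00 | 70.4% | 5.0% | 70.2% |
| 0.25 | 1.03 | 68% | 4.4% | 70.2% |
| 0.5 | 1.12 | 61% | 2.9% | 70.2% |
| 0.75 | 1.26 | 51% | 1.5% | 70.2% |

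**Uneven completers.** Randomised withdrawals are not replaced and further slots are added in tens (7.2, 9.3). Technical failures can remove a participant from an analysis (9.4.1). So 12:12 is not guaranteed. The bias is delta × (n1 − n2)/n. At 15:9 and delta = 0.5 it is 0.5 × 6/24 = 0.125 SD, and 0.125/0.532 = 23% of the expected effect. Size at delta = 0.5 is 3.2% at 13:11, 4.2% at 14:10 and 5.9% at 15:9. Weighting the two orders equally removes the bias. Its standard error at 15:9 is √[(1/15 + 1/9)/4] = 0.211 against 0.204, and power is 67%.

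**Side effects (9.4.5).** The outcome is one rating per session, with nothing subtracted. A plain change s between sessions, such as habituation, moves the dlPFC − mPFC difference by +s in one order group and −s in the other, so the same algebra applies without needing a pattern interaction.

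**Block carry-over (optional check).** The 6.3 rules allow 6 × 4 = 24 block orders. Over these each pattern has 48 blocks: 8 come first and 20 follow each of the other two patterns. If a fraction L of a block's effect persists through the next block, DB − TG is multiplied by 1 − (20/48)L = 1 − (5/12)L. For L = 0.1, 0.25 or 0.5 the multiplier is 0.96, 0.90 or 0.79, and power at dz 0.532 is 67%, 61% or 51%. If full carry-over reached only the first 1, 2 or 5 of 30 trials, the contrast would lose 1.4%, 2.8% or 6.9%.

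**The case against.** The plan argues its case rather than ignoring it. Effects are expected to be brief, trains are at least 11 seconds apart (4.3), both orders are randomised, and 6.3 relies on within-session contrasts to deal with differences between sessions. For additive differences that reliance is fully justified.

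Three stronger readings are tempting and are not supported:

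- A reader might infer that any session-order effect, such as learning or fatigue, inflates the error of the primary contrast. It does not; only an effect that differs by pattern does, and the documents give no evidence of one.
- A reader might infer that leaving out order inflates false positives. At 12:12 the test is conservative, and at delta = 0.5 SD the size is still below 5% at 14:10.
- A reader might take block carry-over as established. The sentence in 9.4.1 concerns sessions, not blocks, and the plan expects carry-over to be near zero. Only the secondary objective's search for a lasting increase in coupling (section 3) sits uneasily with an effect of a second or two.

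The trial is also a pilot that treats a non-significant result as inconclusive. What survives is narrower: a randomised factor is unused, the stated safeguard does not reach the hypothesised contrast, and the covariate clause does not commit to either order or session.

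**Conclusion.** The point holds as a low-cost improvement, not as a flaw that invalidates the analysis. Without the order term, a session-by-pattern shift of 0.25 to 0.75 contrast SD would take power from about 70% to between 68% and 51%. With balanced orders the cost is power only. Bias needs both such a shift and uneven orders. These sizes rest on dz = 0.532, 24 completers and assumed values of delta. The side-effect comparison needs the order term more plainly, because there an ordinary session effect is enough. A preceding-block model is optional, since L is assumed and the plan gives reasons to expect it to be small.

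**What to change.** In 9.4.2 and 9.4.3, add site order (dlPFC-first or mPFC-first) as a between-participant factor with its interactions, and define the site-by-type effect as the equally weighted mean over the two orders. In 9.4.5, do the same for the dlPFC-versus-mPFC comparison. In that linear model the site-by-order term, which is the session effect, must be included, because an order main effect alone would not absorb a change between sessions. State the completer count in each order when reporting. In 9.4.1, say that arrhythmic subtraction does not act on the site-by-type interaction.

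The cost is SAP wording and one degree of freedom: 70.4% to 70.2% power at 12:12 if there is no order effect. With uneven orders, equal weighting costs a little more (standard error about 3% larger at 15:9).

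Optionally, pre-specify one sensitivity model on the 12 block values per person with pattern, site, session and preceding-block pattern. It uses data already collected but is less precise, so it should not replace the main analysis.

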9.4.2 ANALYSIS OF THE PRIMARY OUTCOME (BEHAVIOR)

Goal-directed behavior will be calculated as the average decision to perform the HARD task. The average of the two blocks for each stimulation conditions will be calculated (three stimulation types by two stimulation sites). A two-way repeated-measures analysis of variance (ANOVA) will be performed using within-participant factor of stimulation type (delta-beta TMS versus theta-gamma TMS; each subtracted by session-matched arrhythmic TMS) and within-participant factor stimulation site (dIPFC TMS versus mPFC TMS). We control for the effect of time with a subtraction of delta-beta TMS versus arrhythmic TMS and theta-gamma TMS versus arrhythmic TMS. In other words, four values are submitted to the ANOVA for each participant.

1. Delta-beta TMS to dIPFC minus arrhythmic TMS to dIPFC
2. Theta-gamma TMS to dIPFC minus arrhythmic TMS to dIPFC
3. Delta-beta TMS to mPFC minus arrhythmic TMS to mPFC
4. Theta-gamma TMS to mPFC minus arrhythmic TMS to mPFC

Thus, only differences from our active control, arrhythmic TMS, are considered meaningfully worth interpretation. We hypothesize to find an interaction between stimulation site and stimulation type in the ANOVA. Post-hoc differences will be investigated using Tukey's method to address multiple comparisons. We hypothesize that the predicted interaction will be driven by an increase in goal-directed behavior for delta-beta TMS to dIPFC. Sensitivity analyses will be conducted to evaluate the specificity of these effects: a similar analysis with reward-evaluation as the dependent variable and we do not expect that delta-beta TMS will have any effect on reward-evaluation.

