9.4.3 ANALYSIS OF THE SECONDARY OUTCOME (ELECTROPHYSIOLOGY)

Delta-beta phase amplitude coupling will be calculated between the phase of delta oscillations (2-3 Hz) in prefrontal electrodes (FCz and surrounding electrodes) and the amplitude of beta oscillations (15- 25 Hz) in left motor electrodes (C3 and surrounding electrodes). The instantaneous phase and amplitude of these oscillations will be calculated by averaging the signal in these two regions of interest, band-filtering the signal to the specified range, and then performing the Hilbert transform on the signal. Phase-amplitude coupling (PAC) is then calculated by creating a hybrid signal using the amplitude of beta oscillations in left motor electrodes and the phase of delta oscillations in prefrontal electrodes:

$$PAC = \left| \frac{\sum_{t=1}^N M * e^{i\theta}}{N} \right|, M \text{ is magnitude of beta oscillations, } \theta \text{ is angle of delta oscillations, } N \text{ is number of time points}$$

The PAC value is normalized by creating a null distribution by randomly shifting the beta timeseries by at least 10% of the number of time points. Then, PAC is calculated between the delta-phase timeseries and each of these randomly shifted beta-amplitude timeseries. Finally, PAC_z is calculated as the z-transformed true PAC value relative to the null distribution.

The average during the decision epoch of each trial of the task during stimulation will be calculated. The average of the two blocks for each stimulation conditions will be calculated (three stimulation types by two stimulation sites). A two-way repeated-measures analysis of variance (ANOVA) will be performed using within-participant factor of stimulation type (delta-beta TMS versus theta-gamma TMS; each subtracted by session-matched arrhythmic TMS) and within-participant factor stimulation site (dIPFC TMS versus mPFC TMS). We control for the effect of time with a subtraction of delta-beta TMS versus arrhythmic TMS and theta-gamma TMS versus arrhythmic TMS. In other words, four values are submitted to the ANOVA for each participant.

1. Delta-beta TMS to dIPFC minus arrhythmic TMS to dIPFC
2. Theta-gamma TMS to dIPFC minus arrhythmic TMS to dIPFC
3. Delta-beta TMS to mPFC minus arrhythmic TMS to mPFC
4. Theta-gamma TMS to mPFC minus arrhythmic TMS to mPFC

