Thus, only differences from our active control, arrhythmic TMS, are considered meaningfully worth interpretation. We hypothesize to find an interaction between stimulation site and stimulation type in the ANOVA. Post-hoc differences will be investigated using Tukey's method to address multiple comparisons. We hypothesize that the predicted interaction will be driven by an increase in delta-beta coupling for delta-beta TMS to dIPFC. Sensitivity analyses will be conducted to evaluate the specificity of these effects: a similar analysis with theta-gamma coupling as the dependent variable and we do not expect that delta-beta TMS will have any effect on theta-gamma coupling.

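### The planned tests in 9.4.2 do not include the comparison with arrhythmic TMS that 9.2 states as the primary claim

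*Combined protocol and SAP*

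**What the plan says.** Section 9.2 introduces the primary outcome with the statement "Rhythmic TMS to lateral frontal cortex at delta-beta frequency will increase goal-directed behavior relative to arrhythmic TMS".

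Section 9.4.2 averages the two blocks per condition, subtracts the arrhythmic value of the same session from delta-beta and from theta-gamma at each site, and puts the four difference scores into a two-way repeated-measures ANOVA (type by site). It says that "only differences from our active control, arrhythmic TMS, are considered meaningfully worth interpretation". The predicted result is: "We hypothesize to find an interaction between stimulation site and stimulation type in the ANOVA". For follow-up, "Post-hoc differences will be investigated using" Tukey's method; the pairs are not listed. The section then adds: "We hypothesize that the predicted interaction will be driven by an increase in goal-directed behavior for delta-beta TMS to" dlPFC.

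Section 9.4.3 repeats the structure for delta-beta coupling: "In other words, four values are submitted to the ANOVA for each participant", with the parallel prediction "We hypothesize that the predicted interaction will be driven by an increase in delta-beta coupling for delta-beta TMS to" dlPFC.

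Two other places bear on this. Section 9.4.1 says "Continuous data will be described using means, standard deviations, and confidence intervals", without tying an interval to any particular contrast. Section 9.1 words the primary hypothesis as a difference between the baseline task and the task under dlPFC stimulation, by type. Baseline data do not enter the ANOVA.

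**The concern.** Subtracting arrhythmic TMS from every score gives the impression that every resulting test is a test against arrhythmic. It is not. When one value is subtracted from two others and those two are then compared, the subtraction has no effect. The effect that 9.4.2 relies on is such a comparison.

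What is at stake is the headline conclusion. The plan could report support for an increase relative to arrhythmic that it never tested, or call inconclusive a real increase that its chosen test cannot see.

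**Working it through.** Notation: DB, TG and AR are the delta-beta, theta-gamma and arrhythmic means; d is dlPFC and m is mPFC. The four submitted values are 1 = DBd − ARd, 2 = TGd − ARd, 3 = DBm − ARm, 4 = TGm − ARm.

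**Step 1. The plan's own power figure.** Inputs from 9.2: partial eta-squared 0.23, dependent t-test effect 0.532, 20 earlier participants, correlation 0.77, N = 24, power above 95%.
- f² = 0.23/0.77 = 0.2987. The default repeated-measures formula with two measurements gives noncentrality 0.2987 × 24 × 2/(1 − 0.77) = 62.3 and power above 99.9%, which agrees with the stated figure.
- Read as a one-degree-of-freedom effect, 0.23 with 20 participants gives F = 0.2987 × 19 = 5.68 and dz = √(5.68/20) = 0.533, matching the quoted 0.532. A paired test with dz 0.532 and N = 24 has 70% power.

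The simulations below take 0.532 as the interaction effect, which is why they show 70% and not the figure in 9.2. The cancellation in step 2 does not depend on this choice.

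**Step 2. Cancellation.**
- Interaction: (1 − 2) − (3 − 4) = (DBd − TGd) − (DBm − TGm).
- Type main effect: (1 − 2) + (3 − 4) = (DBd − TGd) + (DBm − TGm).

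ARd and ARm have weight zero in both. In one simulated data set of 24, the interaction F was 0.624 (p = 0.438) with subtraction, without subtraction, and after the arrhythmic scores had been heavily altered. Altering those scores moved only the site effect (F from below 0.001 to 7.22).

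**Step 3. The Tukey pairs.**

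| Pair | Reduces to | Arrhythmic |
|---|---|---|
| 1 v 2 | DBd − TGd | absent |
| 3 v 4 | DBm − TGm | absent |
| 1 v 3 | (DBd − DBm) − (ARd − ARm) | between-site difference only |
| 1 v 4 | (DBd − TGm) − (ARd − ARm) | between-site difference only |
| 2 v 3 | (TGd − DBm) − (ARd − ARm) | between-site difference only |
| 2 v 4 | (TGd − TGm) − (ARd − ARm) | between-site difference only |

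The claim in 9.2 is value 1 against zero. Every pair and every ANOVA effect weights the four values so that the weights sum to zero. Value 1 alone does not, so no combination of these tests equals it.

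**Step 4. What follows at N = 24.** Assumptions: equal variances and correlations, two-sided 0.05, 40,000 simulated trials per case, and each moved condition shifted by the amount that gives interaction dz 0.532 when it moves alone. For value 1 the same shift gives dz = √2 × 0.532 = 0.752, because its standard deviation is smaller by a factor of √2.

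| Truth | Interaction, predicted direction | Value 1 against zero, increase | Both |
|---|---|---|---|
| DB raises the outcome at dlPFC | 70% | 94% | 68% |
| DB inert at dlPFC; TG up at mPFC, or TG down at dlPFC, or DB down at mPFC | 70–71% | about 2.5% | 2.2–2.4% |
| DB and TG both raise it equally at dlPFC | 2.5% | 94% | 2.5% |

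The interaction has the same chance of success in the first two rows, so it cannot by itself say which condition drives it. In the third row the claim in 9.2 is true, and the interaction misses it.

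**Step 5. Section 9.4.3.** The algebra is identical. The secondary statement in 9.2 predicts stronger coupling but does not mention arrhythmic TMS. The conflict in 9.4.3 is therefore with its own interpretation rule and its prediction of what drives the interaction.

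**The case against.** **The post-hoc step may be enough.** Pairs 1 v 2 and 1 v 3 read together do screen out the cases in which delta-beta is inert at dlPFC. Requiring the interaction and both pairs (pooled-error Tukey, an assumption because the plan gives no error term) leaves under 1% false claims in each of the three. This stands. But the plan does not say which pairs must hold, and neither pair compares delta-beta with arrhythmic within dlPFC.

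**Tukey could be read over all six conditions.** Section 9.4.2 does compute six averages, and a six-condition Tukey would include the missing comparison. But the text submits four difference scores to the ANOVA and describes no six-condition analysis. An interval for value 1 would also answer the question, yet 9.4.1 promises intervals only in general.

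**The site-by-type interaction is the right test for specificity.** Agreed. A reader might go further and infer that it is invalid, or that the plan is likely to produce a false claim. The documents support neither: the 70% describes what the interaction alone can show under assumed single-condition shifts, and the post-hoc pairs would catch those cases if they were used. A reader might also infer that 9.4.3 contradicts the secondary statement in 9.2. It does not, because that statement names no comparator.

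**This is a pilot.** True, but the repair needs no new data, and the protocol itself relies on pre-specified analyses to limit bias.

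**Conclusion.** The point holds. The plan as written specifies no test of the primary claim in 9.2, and the interpretation rule in 9.4.2 points to a comparison that the interaction does not contain. The cancellation is exact and needs no assumption. The rates in step 4 rest on equal variances and correlations and on 0.532 as the interaction effect.

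A significant interaction supports specificity of site and frequency. It does not by itself show an increase from delta-beta at dlPFC, and a non-significant one does not rule out an increase relative to arrhythmic. This should be fixed before analysis. It is a gap in what is specified, not a fault in the design or the data.

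**What to change.** Keep the interaction as the test of site and frequency specificity, and add to 9.4.2:

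- Value 1 (delta-beta minus arrhythmic at dlPFC) is tested against zero with a two-sided paired t-test at 0.05. Its mean and 95% confidence interval are reported whatever the interaction shows.
- This contrast supports the claim of an increase relative to arrhythmic TMS.
- A site- and frequency-specific increase driven by delta-beta at dlPFC is claimed only if the interaction and this contrast are both significant in the predicted direction.

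The two claims should stay separate. If the interaction were also required for the plain claim, that claim would be made in only 2.5% of trials in the third row of step 4, where it is true.

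Add the parallel text to 9.4.3 for delta-beta coupling. In 9.2, name the contrast and give its power at N = 24. The documents give no effect size for it, so this has to be a stated assumption: 47%, 70% and 96% at dz 0.4, 0.532 and 0.8. Align the baseline-referenced hypothesis in 9.1 with these contrasts.

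The cost is text only, with the same data and the same N. No alpha split is needed between the two claims, because both require value 1 to be significant. The downside is that the specific claim has less power than the interaction alone. With the interaction at dz 0.532 (70%), joint power is 37%, 54% and 69% for those three values, taking a correlation of 1/(2√2) = 0.354 between the contrasts.
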